3.2.2. Herpes Zoster in Solid Organ Transplant subjects

SOT subjects represent a distinct group of subjects with regard to their CMI. Most SOTs are allogeneic, that is the transplantation of organs with a different genotype from one individual to another. Transplant subjects receive immunosuppressive therapy,

CONFIDENTIAL212340 (ZOSTER-073 EXT:041 Y4-10)
Protocol Amendment 1 Final

chronically, to prevent rejection of these genetically different engrafted organs [EMA, 2008].

Secondary to their CIS, SOT subjects are at increased risk of developing HZ. Three large SOT studies from North America indicate HZ incidence rates in transplant subjects of approximately 8 to 9 times the 3.2 per 1000 person-years estimated for the general US population [Insinga, 2005]. A large single center study from the University of Alberta Hospital, Edmonton, Canada, which included 869 SOT subjects, reported the percentage of subjects with HZ following transplantation of 8.6% for overall SOTs and 7.4% for RTs. The mean time of HZ onset post-transplantation was 13.9 months for SOTs and 15.5 months for RT subjects. The overall HZ incidence rate in SOT subjects was 27.2 per 1000 person-years [Gourishankar, 2004]. Another single center study, conducted at the Mayo Clinic, in Rochester, Minnesota, of 612 RTs, reveals a HZ incidence rate of 28 per 1000 person-years following transplantation. Furthermore, subjects younger than 60 years had an incidence rate of 23 per 1000 person-years whereas subjects of 60 years or more had an incidence rate of 41 per 1000 person-years [Arness, 2008]. A large multicenter study conducted by the US Department of Veterans Affairs of 1077 SOT subjects reported the percentage of HZ of 8.3% overall and 9.0% for RTs. The HZ incidence rate for SOT was 22.2 per 1000 patient-years and for RT subjects was 24.4 per 1000 patient-years. Multivariate modelling revealed that African Americans and older transplant subjects had increased relative hazards of HZ [Pergam, 2011].

The increased incidence rate of HZ within SOT subjects on CIS establishes the basis for evaluating GSK's candidate HZ/su vaccine in this population.

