Visit 1 – Visit 2	[330-415 days]	
Target: [180-540 days]
 
The start of the interval may be moved by up to 6 months (starting no later than 18 months post-Visit 1)
	Any interval as informative for LTFU
Visit 1 – Visit 3	[690-775 days]	
The start of the interval may be moved by up to 6 months (starting no later than 30 months post-Visit 1), e.g., to avoid potential seasonal recurrence of COVID-19.
 
[510-985 days]
 
For delayed enrolled subjects, there is no strict interval. Ideally, there would be at least 6 months between their combined Visit 1/Visit 2 and Visit 3, but this is not required. The latest timepoint for Visit 3 to occur for delayed enrolled subjects would match the latest timepoint of all other previously enrolled subjects' Visit 3 so that all subjects can be revaccinated contemporaneously. The goal is to maintain similar revaccination follow-up
	Any interval as informative for LTFU

		timing so as not to delay study end.	
Visit 3 – Visit 4	[30-60 days]	[30-182 days]	[25-90* days]
Visit 4 – Visit 5	[30-48 days]	[30-90 days]	[25-90* days]
Visit 4 – Visit 6	[330-415 days]	[330-445 days] The allowed interval for Visits 6 should be the same for both the re-vaccinated and non-revaccinated subjects.	Any interval as informative for LTFU
Visit 4 – Visit 7	[690-775 days]	[690-805 days] Visit 7 may be Scheduled earlier to make up for delays incurred during times of special circumstance, in order to maintain planned duration of the study. Delayed or cancelled if special circumstances preclude the original planned visit. The allowed interval for Visit 7 should be the same for both the re-vaccinated and non-revaccinated subjects.	Any interval as informative for LTFU

Additionally, out-of-window visits are expected due to COVID-19 pandemic issues that do not fall into the “special circumstances” as just described, e.g., reduced clinic hours or patient capacity, but not the “clinics closed” requirement to enact special circumstances provisions. Determination of elimination, or not, for these out-of-window visits will take place during DMR pre-analysis.

Official elimination will take place during DMR in the pre-analysis meeting as the intervals for PPS eligibility may need to be adjusted or expanded further as the goal is to get as much immunogenicity and LTFU data as possible in this small sample size.

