4.3.2.1. Long-term follow-up phase

The results for the analysis of safety in the long-term follow-up phase will be tabulated as follows:

- Number and percentage of subjects reporting at least one SAE related to primary vaccination in study ZOSTER-041 classified by Medical Dictionary for Regulatory Activities (MedDRA) Primary System Organ Class (SOC) and Preferred Term (PT) from the day after

ZOSTER-041 last study visit (Month 13) to ZOSTER-073 pre-revaccination (Visit 3 Month 24) will be tabulated with exact 95% CI.

- Number and percentage of subjects with at least one suspected or biopsy-proven allograft rejection from ZOSTER-041 last visit (Month 13) to ZOSTER-073 Day 1 will be tabulated with exact 95% CI.
- Number and percentage of subjects with at least one biopsy-proven allograft rejection from ZOSTER-073 Day 1 to ZOSTER-073 pre-revaccination (Visit 3 Month 24) will be tabulated with exact 95% CI.
- Number and percentage of subjects with suspected or confirmed HZ cases from ZOSTER-041 last visit (Month 13) to study ZOSTER-073 Day 1 will be tabulated with exact 95% CI.
- Number and percentage of subjects with confirmed HZ cases from ZOSTER-073 Day 1 through ZOSTER-073 study Month 24 will be tabulated with exact 95% CI.
- Listing of subjects with history of suspected allograft rejection or history of biopsy-proven allograft rejections from ZOSTER-041 last study visit to ZOSTER-073 Day 1 will be provided.
- Listing of subjects with biopsy-proven allograft rejections from ZOSTER-073 Day 1 onward will be provided.
- Listing of subjects with a suspected or confirmed HZ episode from ZOSTER-041 last study visit to ZOSTER-073 Day 1 will be provided.
- Listing of subjects with a confirmed HZ episode from ZOSTER-073 Day 1 onward will be provided.
- Number of subjects with declining allograft function (following HZ and allograft rejection episodes), as determined by fold change from baseline serum creatinine measurements, for the time period from study ZOSTER-041 last visit (Month 13) to study ZOSTER-073 Visit 3 (Month 24). This serum creatinine fold change from baseline will be summarized descriptively. A list of subjects with an increase in serum creatinine will also be presented. Allograft dysfunction is defined as having a fold increase in serum creatinine of 1.2 or greater from the reference timepoint.

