- Number and percentage of subjects with at least one pIMD classified by MedDRA Primary SOC and PT and percentage of subjects with at least one pIMD with causal relationship, reported from revaccination Dose 1 up to 30 days, from revaccination Dose 1 up to 12 months post-last revaccination dose, and from revaccination Dose 1 up to study end will be tabulated with exact 95% CI.
- Number and percentage of subjects with at least one biopsy-proven allograft rejection and biopsy-proven allograft rejection with causal relationship reported from revaccination Dose 1 up to study end will be tabulated with exact 95% CI.
- Number and percentage of subjects with at least one biopsy-proven allograft rejection and biopsy-proven allograft rejection with causal relationship reported from revaccination Dose 1 up to 12 months post last revaccination will be tabulated with exact 95% CI.
- Number and percentage of subjects with fatal SAEs and causally related fatal SAEs classified by MedDRA Primary SOC and PT will be presented. Fatal SAEs and related fatal SAEs will also be described by onset date of SAE and date of death as follows:
 - With onset date of fatal SAE during the period starting from revaccination Dose 1 to 30 days post last revaccination dose, from revaccination Dose 1 up to 12 months post last revaccination, and from revaccination Dose 1 up to study end

[figure not shown]
- Who died (date of death) during the period starting from revaccination Dose 1 up to 30 days post last revaccination dose, from revaccination Dose 1 up to 12 months post last revaccination, and from first revaccination to study end.
- SAEs and pIMDs will be listed. These listings will include all fields on the CRF, including but not limited to, verbatim event description, MedDRA SOC/PT, start/stop study days, site, intensity (maximum and at time of onset), relationship to study vaccine, outcome.
- Listing of withdrawals due to AE and SAEs will be provided, including verbatim event description, MedDRA SOC/PT, start/stop study days, site, intensity (maximum and at time of onset), relationship to study vaccine, outcome
- Listing of subjects with confirmed HZ episode from Dose 1 of revaccination (Month 24) up to study end will be provided.

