4.5.3.4. HZ Episodes

Suspected episodes of HZ will be identified via the HZ episode status eCRF.

Confirmed episodes of HZ will be identified via Polymerase Chain Reaction (PCR) test on HZ lesion sample.

The number of subjects with HZ episodes will be tabulated as follows:

- From ZOSTER-041 last visit (Month 13) to ZOSTER-073 Day 1
- From ZOSTER-073 Day 1 through ZOSTER-073 study Month 24
- From first revaccination up to study end

The number and percentage of non-revaccinated subjects reporting the occurrence of HZ episodes from visit 3 (Month 24) up to study end will also be presented.

All suspected and confirmed HZ episodes occurring between the end of ZOSTER-41 and ZOSTER-073 enrollment and occurring after ZOSTER-073 will be listed.

Immunosuppressive therapies before, during, and after the episode will be listed for subjects with HZ episodes in the concomitant medications listing.

GMCs of anti-gE antibody and CD4+T-cells secreting at least 2 activation markers in subjects who had suspected and/or confirmed HZ episodes will be displayed graphically. Values taken before and after the episode will be indicated using different colors and symbols in the figure.

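### Herpes zoster is summarised per subject with no person-time, although follow-up is unequal, so the percentages mix risk with length of observation

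*SAP*

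**What the plan says.** For the gap between the studies, SAP 4.3.2.1 plans "Number and percentage of subjects with suspected or confirmed HZ cases from ZOSTER-041 last visit (Month 13) to study ZOSTER-073 Day 1", with an exact 95% interval. For the long-term follow-up phase it plans subjects with "confirmed HZ cases from ZOSTER-073 Day 1 through ZOSTER-073 study Month 24 will be tabulated with exact 95% CI". For the revaccination phase, SAP 4.3.2.2 plans a listing: "Listing of subjects with confirmed HZ episode from Dose 1 of revaccination (Month 24) up to study end will be provided".

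SAP 4.5.3.4 then states "The number of subjects with HZ episodes will be tabulated as follows" and names the gap, Day 1 to Month 24, and first revaccination to study end. It also plans "The number and percentage of non-revaccinated subjects reporting the occurrence of HZ episodes from visit 3 (Month 24) up to study end". All suspected and confirmed episodes are listed.

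On follow-up, SAP 1.2 says the interval between the two studies varies by subject. SAP 3.1 says of late entrants: "For delayed enrolled subjects, there is no strict interval". SAP 4.5 states that non-revaccinated subjects will be compared with revaccinated subjects after Visit 3.

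For context, Protocol 3.2.2 cites a renal transplant cohort that "reveals a HZ incidence rate of 28 per 1000 person-years following transplantation", along with other rates and some raw percentages.

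**The concern.** A percentage of subjects is a cumulative risk over whatever time each subject was observed. When observation time differs between subjects and between windows, two percentages can differ with no difference in underlying rate. The sponsor recognises uneven timing for immunogenicity, where SAP 1.2 regroups visits by years since dose 2. HZ gets no equivalent.

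Three readings are affected: one window against another, revaccinated against non-revaccinated subjects after Visit 3, and this cohort against the per-person-year rates in Protocol 3.2.2. No hypothesis test is at stake. The question is whether a secondary endpoint can be interpreted as tabulated.

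**Working it through.** **Planning figure.** Neither document states an HZ rate, person-time or precision for this study. The nearest stated figure, 86 × 0.85 = 73.1, reproduces the roughly 73 subjects evaluable for humoral immunogenicity, but it has no bearing on HZ. The calculations below use the 68 subjects enrolled (SAP Table 1).

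**Length of each window**
- *Gap.* It starts at ZOSTER-041 Month 13, which is 12 months after dose 2. It ends at the first ZOSTER-073 visit, which SAP 1.2 bins from 3.5 to below 6.5 years. Hence 3.5 − 1 = 2.5 years to 6.5 − 1 = 5.5 years, a ratio of 2.2. These are bin edges, so this is an outer limit. Protocol Table 3 places Visit 1 at about 4 to 5 years, giving a gap of about 3 to 4 years.
- *Day 1 to Month 24.* SAP 3.1 allows 510 to 985 days under special circumstances (ratio 1.93), against 690 to 775 originally (1.12). Delayed enrollees have Visits 1 and 2 on one day (Protocol 8.1.16), and six months to Visit 3 is preferred but not required. I assume 0.5 year as an example.
- *First revaccination to study end.* Amended intervals give 30 + 690 = 720 to 182 + 805 = 987 days (1.37). Original intervals give 720 to 60 + 775 = 835 days (1.16). If Visit 7 is cancelled and follow-up stops at Visit 6, the minimum is 30 + 330 = 360 days (987/360 = 2.74).

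**Expected percentage at one constant rate.** Risk = 1 − exp(−rate × years). The rate is 24.4 per 1000 person-years, one of the renal transplant rates in Protocol 3.2.2.

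| Window | Shortest | Longest |
|---|---|---|
| Gap, outer limits (2.5 to 5.5 years) | 5.9% | 12.6% |
| Gap, nominal schedule (3 to 4 years) | 7.1% | 9.3% |
| Day 1 to Month 24 (510 to 985 days) | 3.3% | 6.4% |
| Same, delayed enrollee at 0.5 year | 1.2% | 6.4% |
| Revaccination to end (720 to 987 days) | 4.7% | 6.4% |
| Same, Visit 7 cancelled (360 days) | 2.4% | 6.4% |

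**One percentage, different rates.** Suppose 5 of 68 subjects report HZ in the gap (an assumed count): 7.4%, exact 95% interval 2.4 to 16.3.
- Mean gap 2.5 years: 68 × 2.5 = 170 person-years; 5/170 = 29.4 per 1000 (9.5 to 68.6).
- Mean gap 4 years: 68 × 4 = 272 person-years; 5/272 = 18.4 per 1000 (6.0 to 42.9).
- Mean gap 5.5 years: 68 × 5.5 = 374 person-years; 5/374 = 13.4 per 1000 (4.3 to 31.2).

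**Direction.** If all 68 had exactly two years from Day 1 to Month 24, person-time would be 136 years. The delayed share is not stated, so I assume two cases and place everyone else's Visit 3 at 2.5 years.
- 30% delayed at 0.5 year: 47.6 × 2.5 + 20.4 × 0.5 = 129.2, below 136.
- 10% delayed at 1 year: 61.2 × 2.5 + 6.8 × 1 = 159.8, above 136.

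The sign therefore depends on dates that the HZ tables do not use.

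**Precision.** At 28 per 1000, 136 person-years gives 3.8 expected cases. Four cases is 29 per 1000, exact Poisson 95% interval 8 to 75.

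**The case against.** The endpoint is occurrence of HZ, and a count over enrolled subjects answers that. Efficacy assessment is marked not applicable (Protocol 8.2), all analyses are descriptive, and neither document promises a comparison with background rates. Protocol 3.2.2 cites those rates as the reason to study the vaccine in this population. It also gives percentages (7.4% to 9.0%), age-specific rates (23 and 41 per 1000) and a general-population rate (3.2). With few cases, the listings and the visit-interval summaries in SAP 6.1.5 would let a reader approximate person-time. A rate would still compare poorly with the cited cohorts: theirs count from transplantation, and gap cases here are retrospective, include suspected HZ, and come only from people who later re-enrolled.

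Most of this stands and limits the point to presentation. It does not remove the comparison of revaccinated with non-revaccinated subjects in SAP 4.5 or the differing lengths of the windows.

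A reader might also infer that the percentages understate HZ risk. The documents do not support that. Late entry and withdrawal shorten follow-up, but Visit 3 may fall as late as 985 days, and the share of delayed enrollees is not stated. Nor do they support treating the 2.2-fold gap spread as observed.

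**Conclusion.** The point holds as a low-cost improvement to a descriptive safety summary; it does not identify an error in a planned test. At a constant rate, follow-up alone could move the expected percentage about twofold in the gap at the outer limits, and about twofold from Day 1 to Month 24 under the amended intervals. For revaccinated subjects who complete, the last window varies only about 1.2- to 1.4-fold. The direction of any distortion is unknown.

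This rests on a constant hazard, on permitted intervals in place of actual dates, and on an assumed 0.5 year for a delayed enrollee. It also rests on the visible text: SAP 4.4 is redacted and could not be checked.

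**What to change.** In SAP 4.3.2.1, 4.3.2.2 and 4.5.3.4, keep the counts, percentages and listings. For each window, and for non-revaccinated subjects after Visit 3, add person-years at risk and incidence per 1000 person-years with an exact Poisson 95% interval. Count each subject's time from the start of the window to first HZ onset, last contact or the end of the window, whichever comes first. Show confirmed cases separately from retrospective suspected cases. State in the table notes that the rates are descriptive and are not an efficacy comparison.

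The cost is a few columns built from visit, onset and last-contact dates already collected; SAP 6.2.5.1 already has rules for partial dates. The drawbacks are wide intervals, because few events are expected, and comparability with the background rates that remains limited.

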4.6. Other Analyses

4.6.1. Subgroup analyses

The primary immunogenicity endpoints will not be presented by subgroup. Subgroup analyses of the secondary safety endpoints will be performed by age group only. If the number of subjects with the particular AE is too small (less than [10%] of the sample size), the safety table may not be provided by age stratum.

If the number of subjects is too small (less than [10%]) within a subgroup, then the subgroup categories may be redefined prior to locking the study. See Table 2 for the subgroup category definitions and presentations.

Sub-groups (endpoint)	Order in tables	Label in tables	Definition for footnote
Age strata (Safety endpoints)	1	18-49ys	Subjects aged between 18 and 49 years
	2	>= 50ys	Subjects aged 50 years and older
Combination of types of maintenance immuno- suppress- ive therapy in use (demography)*\$	1	All 3 classes: CIS + CS + MC	Subjects using calcineurin inhibitor or sirolimus, corticosteroids and mycophenolate compound as maintenance immunosuppressive therapy at Visit X
	2	Any 2 class combinations of CIS, CS, or MC	Subjects using any combination of any two of three classes of immunosuppressant: 1) Calcineurin or mTOR inhibitors such as cyclosporine, sirolimus, or tacrolimus, everolimus; 2) Corticosteroids such as prednisone; and 3) Mycophenolate compounds as maintenance immunosuppressive therapy at Visit X
	3	Any single class: CIS, CS, or MC	Subjects using any single class of immunosuppressant: 1) Calcineurin or mTOR inhibitors such as cyclosporine, sirolimus, or tacrolimus, everolimus; 2) Corticosteroids such as prednisone; and 3) Mycophenolate compounds as maintenance immunosuppressive therapy at Visit X

* The combination of types of immunosuppressive therapy that are not applicable will not be displayed in the statistical tables. \$Visit X will be replaced with the primary vaccination visit, or first revaccination visit as applicable, per phase.

4.6.2. Sensitivity Analyses

4.6.2.1. Dialysis Recipients

Subjects who receive dialysis after revaccination will be excluded from the primary and secondary analyses as part of the elimination criteria defined in Section 3.1. Summaries of GMCs of anti-gE antibody, anti-gE antibody seropositivity rates with 95% CI, and frequency of

gE specific CD4+T-cells secreting at least 2 activation markers (among IFN- γ , IL-2, TNF- α , CD40L) will be provided separately for dialysis recipients for the revaccination follow-up phase. An additional sensitivity analysis may be performed in which these subjects' results are included with the rest of the PPS for persistence after revaccination course (revaccination follow-up phase).

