Code	Condition under which the code is used	Analysis set eliminated from	Visit (timepoints) where the code is applicable	Type of Elimination
	revaccinated without fulfilling the eligibility criteria for revaccination	(revacc. follow-up phase)		
2040	Administration of any concomitant medication(s) forbidden by the protocol	PPS (revacc. active phase), PPS (revacc. follow-up phase)	Visit 1 – Visit 7	Eliminate from Visit(s) only, as applicable
2050	Underlying medical condition forbidden by the protocol, or some Intercurrent medical conditions (IMCs). (To be determined before analysis during data management review (DMR))	PPS (LTFU), PPS (revacc. active phase), PPS (revacc. follow-up phase)	Visit 1 – Visit 7 (visit and onward)	Eliminate from Visit and onwards
2060	Concomitant infection related to the revaccination which may influence immune response – For example, clinically diagnosed suspected HZ cases before Visit 1 or PCR confirmed HZ cases after Visit 1	PPS (LTFU), PPS (revacc. active phase), PPS (revacc. follow-up phase)	Visit 1 – Visit 7	Eliminate from Visit(s) only, as applicable
2070	Concomitant infection not related to the vaccine which may influence immune response – For example, in case of revaccination, any additional confirmed or suspected immunosuppressive or immunodeficient condition (e.g., malignancy, hepatitis, HIV infection, systemic infection)	PPS (LTFU), PPS (revacc. active phase), PPS (revacc. follow-up phase)	Visit 1 – Visit 7	Eliminate from Visit and onwards
2080	Out of window treatment administration – Revaccination dose 1 (study Month 24) to revaccination dose 2 (study Month 25) outside 25-90 day interval	PPS (revacc. active phase), PPS (revacc. follow-up phase)	Visit 3 – Visit 4	Eliminate from Visit and onwards
2090	Missed Visit, excluding phone contact Note: this does not apply to delayed enrolled subjects who had their Visit 1 and Visit 2 on the same day.	PPS (LTFU), PPS (revacc. active phase), PPS (revacc. follow-up phase)	Visit 1 – Visit 7	Eliminate from Visit only
2090	Assessment not properly performed – For example, incomplete assessment, missed assessment except safety follow-up Note: this does not apply to delayed enrolled subjects who had their Visit 1 and Visit 2 on the same day. These subjects would have to have an assessment at either Visit 1 or Visit 2.	PPS (LTFU), PPS (revacc. active phase), PPS (revacc. follow-up phase)	Visit 1 – Visit 7	Eliminate from Visit only

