4.3.2. Secondary safety endpoints

Safety analyses will be performed on the Enrolled Set for the LTFU phase and the ES for the revaccination phase. All analyses of solicited and unsolicited AEs will be performed overall and by age stratum (based on age at the time of primary vaccination in ZOSTER-041 for the LTFU phase, based on age at the time of revaccination in ZOSTER-073 for revaccination active and follow-up phases).

If the number of subjects with the particular AE is too small (less than [10%] of the sample size), the safety table may not be provided by age stratum.

For solicited AE summaries, the denominators used for deriving percentages will include all revaccinated subjects with at least one solicited local or solicited general symptom documented as either present or absent.

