- Listing of subjects with biopsy-proven allograft rejection from Dose 1 of revaccination (study Month 24) up to study end will be provided. For subjects with an episode of biopsy-proven rejection, dates of biopsy-proven rejection episodes, treatment given (including dialysis), intensity, and rejection outcome will be included in the listing of renal transplant rejection history.
- Number and percentage of subjects with declining allograft function (following revaccination, HZ episode, and allograft rejection), as determined by serum creatinine measurements. Serum creatinine values will be summarized descriptively. See Section 4.5.3.1 for more details. Allograft dysfunction is defined as having a fold increase in serum creatinine of 1.2 or greater from the reference timepoint.

The listings will contain all events (HZ episodes, rejections) and columns will be included to indicate timing (up to Day 1, Before revaccination, et.)

CC1

CCI

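### SAP 4.6.2.1 excludes whole subjects for dialysis after revaccination by pointing to a Section 3.1 criterion that does not exist, with no visit limit and only an optional, partial re-inclusion

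*SAP*

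**What the plan says.** The rule is in SAP 4.6.2.1, under sensitivity analyses. Its first sentence begins "Subjects who receive dialysis after revaccination will be excluded from the primary and secondary analyses" and goes on to place this exclusion under the Section 3.1 criteria. The rest of that section deals with immunogenicity only. Summaries of anti-gE GMCs, seropositivity rates and CD4[2+] frequencies "will be provided separately for dialysis recipients for the revaccination follow-up phase". Then "An additional sensitivity analysis may be performed" that puts these results back into the per-protocol set (PPS) for the follow-up phase.

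SAP 3.1 lists each elimination code with the analysis sets and visits it affects. No code names dialysis. The nearest is 2050, which covers forbidden underlying conditions and some intercurrent medical conditions. Its use is left to the data management review. It affects the three PPS only, and its stated scope runs from the affected visit onwards. Section 3.1 also lets that review decide, for any code, whether it applies to all visits, one visit, or a visit and later.

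For safety, SAP 4.3.2 states: "Safety analyses will be performed on the Enrolled Set for the LTFU phase and the ES for the revaccination phase". SAP 3 puts every subject with at least one dose in this study into the Exposed Set (ES). The secondary safety tabulations in SAP 4.3.2.2 include "Number and percentage of subjects with declining allograft function (following revaccination, HZ episode, and allograft rejection), as determined by serum creatinine measurements", and the rejection listing there shows dialysis among the treatments given.

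Protocol 8.1.14 lists the start of dialysis under the management of rejection. Dialysis is not named in protocol 7.5.2 or 7.6 as a ground for leaving the per-protocol analyses, and SAP 4.8 does not record the rule as a change.

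**The concern.** The exclusion depends on something that happens after dosing and that the protocol associates with rejection. It is stated for subjects, not for samples, and has no time limit within the revaccination period. A subject with valid samples before and one month after each revaccination dose could therefore be removed from the primary active-phase results because of an event many months later. The remaining subjects would be partly selected on how their grafts fared.

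The reference to Section 3.1 should settle scope and timing, but it leads to no dialysis criterion. Two statisticians could follow the SAP faithfully and produce different per-protocol sets. The sentence also speaks of primary and secondary analyses without limiting itself to immunogenicity, although in this SAP the secondary endpoints include safety.

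**Working it through.** **1. Numbers available.** The plan's evaluable target reproduces: 86 × (1 − 0.15) = 73.1, given as about 73 (SAP 5). The point does not rest on it. The relevant count is the 68 subjects actually enrolled (SAP 1.2, Table 1). The number revaccinated is not given, so 68 is its upper bound. No count of dialysis recipients is given either.

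**2. Which sets can a Section 3.1 code reach?**
- Codes 800 (fraudulent data) and 900 (invalid consent) apply to all sets.
- Code 1030 (not revaccinated) applies to the ES and the two revaccination PPS.
- Every other code applies to PPS only.

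A dialysis recipient coded 2050 therefore leaves the PPS from the affected visit and stays in the ES.

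**3. Which samples go?** Take a subject revaccinated at Visits 3 and 4 who first needs dialysis between Visits 6 and 7.

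| Reading | Revaccination-period visits removed | Visits kept |
|---|---|---|
| Code 2050, default scope | 7 | 3, 4, 5, 6 |
| 4.6.2.1 taken literally | 3, 4, 5, 6, 7 | none |

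The difference is four valid samples. Three of them (Visits 3, 4 and 5: Months 24, 25 and 26) are at primary timepoints.

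**4. Do the other displays recover them?** The separate summaries for dialysis recipients and the optional re-inclusion are both defined for the follow-up phase (Months 37 and 49). Neither covers Months 25 and 26.

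**5. Does the 5% rule recover them?** SAP 4.2 adds an Exposed Set analysis for the active phase if 5% or more of subjects with serology are eliminated. Protocol 10.3.3 has the same rule for the follow-up phase. The smallest number of eliminations k that meets it is 0.05 × N rounded up, where N is the number of subjects with serology.

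| N (assumed) | 0.05 × N | k needed |
|---|---|---|
| 68 | 3.4 | 4 |
| 60 | 3.0 | 3 |
| 50 | 2.5 | 3 |
| 40 | 2.0 | 2 |

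At 68: 1/68 = 1.5%, 2/68 = 2.9%, 3/68 = 4.4% and 4/68 = 5.9%. One to three eliminations miss the trigger if nobody else with serology is eliminated.

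**6. What cannot be computed.** The documents give no standard deviation and no expected difference in antibody level between dialysed and other subjects. The effect on the GMC therefore cannot be sized from them.

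**The case against.** The best defence is that 4.6.2.1 works only through Section 3.1. If dialysis is handled under code 2050, the default scope keeps every sample before the affected visit, and the sentence is merely loose. The separate follow-up summaries are promised, not optional. With fewer revaccinated subjects, or with eliminations for other reasons, the 5% rule may well be met: three of 60 is exactly 5.0%. All of this is fair. But assigning dialysis to code 2050 is an inference, the data management review may set a different scope, and the active phase has no dialysis-specific display.

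A reader might infer something stronger: that dialysed subjects, and with them the graft failures, would disappear from the rejection, allograft dysfunction and SAE tables. The words primary and secondary analyses literally reach that far. The documents do not support it as a plan. The sentence is tied to Section 3.1, where no code of this kind reaches the ES. Safety is run on the Enrolled and Exposed Sets, protocol 7.6 confines intercurrent conditions to immunologic assessments, and the rejection listing expects to show dialysis.

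It would also go too far to say that immunogenicity is reported only in subjects whose grafts did well. Follow-up results for dialysis recipients will be shown separately, and rejection without dialysis is not excluded by this sentence.

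**Conclusion.** The defect is an over-broad and unresolved exclusion rule for immunogenicity. As written, it permits removal of valid pre-dialysis samples at the primary Month 24 to 26 timepoints on the basis of a later event linked to rejection, and it contradicts the visit-onwards scope of the nearest code. Up to four valid samples per affected subject depend on which reading is applied, in the example of dialysis first needed between Visits 6 and 7. The number of such subjects is unknown. If all 68 were revaccinated and had serology, and there were no other eliminations, one to three of them would go without any mandatory inclusive analysis.

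On safety, the finding is only that the unqualified wording conflicts with the ES rules. Removal of graft failures from the safety tables is not shown to be planned, so no change in a rejection rate should be attributed to it.

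**What to change.** 1. In SAP 4.6.2.1, limit the exclusion to the immunogenicity PPS analyses and to visits after dialysis starts. Add a code to Section 3.1 with the same sets and visit scope, so that the reference leads to a real criterion.
2. State in the same place that the Enrolled and Exposed Set safety analyses keep these subjects.
3. Change the inclusive immunogenicity sensitivity analysis from *may* to *will*, and extend it to the revaccination active phase.

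The cost is a few sentences of SAP text and one or two extra tables. The analysis is descriptive, so no sample size or error rate is affected.
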